11.2 Subject confidentiality

11.3 Subject privacy

11.4 Data disclosure

11.5 Protected Health Information/Data Protection

11.6 Data safety and monitoring

11.7 Risk/benefit

11.7.1 Potential study risks

11.7.2 Potential study benefits

11.7.3 Risk/benefit assessment

1. Abstract

Many older adults are at risk of illness, hospitalization, and death from vaccine-preventable diseases. More than half of older adults in the United States are not vaccinated for flu which has remained relatively constant over the past decade, and there are racial, ethnic, and socioeconomic disparities in care. In this study, we will evaluate personalized nudges to clinicians and patients to help increase flu vaccination rates during primary care visits among older adults at three distinct health systems, with a particular focus on population subgroups at high risk for vaccine noncompletion. In a partnership between Penn Medicine and University of Washington (UW) Medicine, this will be a 6-month, multisite, cluster randomized, pragmatic trial with an additional intensification arm for high-risk patients. We will also perform a 6-month replication trial at Lancaster General Health.

2. Overall objectives

The objectives of the study are to:

- 1) To conduct a 6-month, multisite, cluster randomized, pragmatic trial to evaluate the effectiveness of personalized nudges to clinicians and patients relative to control to improve flu vaccine completion among older adults.
- 2) To evaluate the effectiveness of an additional, intensification nudge intervention on reducing disparities in flu vaccine completion among high-risk subgroups.
- 3) To evaluate heterogeneity in treatment effect across clinician, patient, and practice characteristics to further tailor approaches in future intervention design.

3. Aims

3.1 Primary Outcome

The primary outcome is flu vaccination completion during the first eligible primary care visit.

3.3 Secondary outcome

The secondary outcome is flu vaccination completion within 3 months after the first eligible primary care visit.

4. Background

Older adults are at risk of serious illness and hospitalization from vaccine-preventable disease.^{1,2} The low vaccination rates have remained relatively stable over the last decade, indicating an urgent need for novel, scalable interventions to increase vaccination rates.³ Further, significant disparities exist relative to who receives a vaccination.⁴ Over 90% of clinicians use the electronic health record to facilitate decision making.⁵ Prior work has demonstrated that EHR-based nudges can increase vaccination ordering rates, cancer screening rates, and statin prescribing.⁶⁻⁹ Building upon our prior work, we propose to use analytical methods to identify older adults at high-risk of flu vaccination non-participation, assess the feasibility of using a set of EHR-based nudge interventions at two primary sites (Penn Medicine and UW Medicine) to improve flu vaccination among older adults, especially those in high-risk groups. We then plan to replicate these findings in a third site, Lancaster General Health.

5. Study design

5.1 Design

This study will be a multisite, cluster randomized, pragmatic trial to evaluate the effectiveness of personalized nudges to clinicians and patients, relative to a control, to increase flu vaccination rates among older adults in accordance with CDC guidelines. This will include clinician and patient level nudge interventions, with additional, intensified nudge interventions for patients identified as high risk for not receiving a flu vaccine.

This cluster randomized trial will randomly assign primary care clinics in a 2:1 ratio to either a nudge interventions or control arm using a covariate-constrained randomization.¹⁰ The intervention arm consists of a multi-component nudge intervention for patients and primary care providers (PCPs). Patients at high-risk for non-completion of the flu vaccine will be randomized to an additional intensification nudge (compared with the multi-component nudge intervention alone).

All patients scheduled for a visit at the clinics randomized to the intervention arm will receive a pre-visit text message sent via Way to Health (a HIPAA compliant, approved platform) that informs the patient the flu vaccine has been reserved for them at their upcoming visit. Those patients that do not have a cell phone in the EHR will receive automated voice recording (AVR). For the patient intensification nudge, we will focus on patient subgroups within the clinic intervention arm that were identified through our previous analyses as high risk for not receiving a vaccine: age ≥ 70 , Black race, residence in lower income communities (lowest quartile according to zip code), or no documented history of flu vaccine in the year prior. Patients who meet these criteria will be randomized 1:1 to receive an additional nudge via a bidirectional text messaging intervention versus no additional nudge. We will translate patient text messages for patients who require an interpreter according to their language preferences in the EHR. Translation will be available for Spanish and up to 4 additional languages based on site specific populations and technical capabilities. Our preliminary work identified the following five languages that account for 97.5% of the expected study sample: English, Spanish, Chinese, Vietnamese, and Russian.

For clinicians within the intervention arm, a flu vaccine order will be pended on their behalf prior to the PCP visit. This will frame vaccination as the default choice (opt-out rather than opt-in) while reducing clinician/care team effort by removing the need to individually order each vaccine. The unsigned order will be visible to the provider during the visit and they will maintain the option to sign or cancel the order.

In addition to the pended order, eligible clinicians within the intervention arm will receive a monthly peer-comparison feedback message describing their flu vaccine completion rate, relative to that of their peers. We will deliver this feedback via email and vary feedback based on clinicians' vaccine completion rates. PCPs whose completion rates are below the median rate will receive feedback relative to the median rate; PCPs whose completion rates are between the median and the 90th percentile will receive feedback relative to the 90th percentile, and those above the 90th percentile will not receive peer comparisons but will get positive feedback that they are high performers. This tiered approach has previously been shown to motivate clinician behavior and prevent regression to the mean among high performers. Figure 1 provides an overview of the study design. We will use this design to replicate our findings at a third site, Lancaster General Health.

[figure not shown]

Figure 1. Overview of study design

5.2 Study sites

Penn Medicine and UW Medicine will be the primary sites for this trial, with Penn serving as the primary IRB site. Lancaster General Health is the study replication site.

5.3 Study duration

The study (including replication) is expected to take 3 years to complete including study preparation (year 1), trial intervention (year 2) and replication (year 3), analysis, and dissemination (year 3). The study intervention will run for 6 months during flu season (September – February).

5.4 Resources necessary for human research participation

The research staff spans the Penn Medicine Center for Health Care Innovation and Department of Medical Ethics and Health Policy to ensure Investigator support. This staff includes a study director, a project manager, research coordinator, and data analysts. To ensure that all staff assisting with research are adequately informed about the protocol and research related duties, the team will meet regularly both internally and with external stakeholders, including all research staff at partner sites University of Washington Medicine and Lancaster General Health, after which meeting minutes and task lists will be distributed. All members of the research team have completed CITI human subjects research training. Additionally, the protocol and related task sheets will be shared on a drive accessible to all staff members. The timeline has been constructed to allow for adequate time to conduct and complete the research. There are adequate facilities to ensure the research can proceed.

5.5 Target population

Patients ≥ 50 years of age in primary care clinics at Penn Medicine, UW Medicine, or Lancaster General Health, who have a scheduled new or return non-urgent/sick PCP visit at one of the study practices during the intervention period (September-February) and are eligible for the flu vaccination based on Health Maintenance data.

5.6 Subjects enrolled by Penn Researchers

Based off our power calculations and preliminary data work, Penn Medicine is expected to enroll approximately 51,152 patients.

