5.7 Subjects enrolled by Collaborating Researchers

UW Medicine plans to enroll approximately 28,705 patients.

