Data on PCPs and their patients at Penn Medicine, UW Medicine, and Lancaster General Health will be obtained from Clarity (Epic's data reporting database). Clinician data includes gender and type of medical degree. Patient information includes demographic information, information about comorbid conditions (including diabetes, hypertension, and chronic kidney disease, and comorbid conditions needed to calculate the Charlson Comorbidity Index), contraindications for flu vaccine, appointment data, and flu vaccination administration.

--Randomization—

Primary care clinic level randomization will occur electronically. We will randomize clinics 2:1 to the nudge arm or control arm using covariate-constrained randomization.¹⁰ Covariate-constrained randomization first enumerates a large number (e.g., 50,000) of possible intervention allocations. Then, a measure of covariate balance is computed with respect to a set of pre-specified covariates for each possible allocation. Finally, from a subset of possible allocations that achieve adequate covariate balance, one is randomly chosen as the final allocation of interventions for the study. We will implement a version of covariate-constrained randomization that stratifies by health system (Penn and UW) and balances the distribution of clinic size and panel risk across arms. The randomization procedure will be implemented in R¹¹ using the cvcrand package.¹² For the replication trial at Lancaster General Health, we will implement covariate-constrained randomization using the cvcrand package to balance the distribution of clinic size and panel risk across arms.

Within the high-risk patient subgroups, stratifying by intervention clinics, patients will be randomized 1:1 in Way to Health using permuted block randomization using random block sizes of 2, 4, and 6 to receive the additional intensification bidirectional text messaging nudge or standard messaging.

9. Analysis plan

Prior to analyses, we will produce data summaries to assess data quality, data distribution, and randomization success. To ensure even comparison across practices and arms, we will classify eligible patients at 4 days before a scheduled appointment for a new or return visit with their primary care clinician as being enrolled in the study. The primary analysis will be performed using an intention-to-treat approach. Specifically, patients who

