do not show up to the first scheduled clinician visit will be considered enrolled and included in the primary analysis.

--Power Calculations--

For the following power calculations, we used an adjusted Type I error of 0.025 to account for two comparisons: 1) clinic-level nudges versus usual care, and 2) intensification for high-risk patients versus no intensification within practices where clinic-level nudges are provided. Based on retrospective data from our health systems, we will have 85% power to detect a 7-percentage point difference in the flu vaccine completion rate for comparison #1. This calculation assumed N=48 participating clinics across the two sites, an average cluster size of n=1385 patients, and an intracluster correlation (ICC) of 0.02. For comparison #2, we will have at least 99% power to detect a 2-percentage point difference even if the rate of vaccination in the high-risk group is 50%, the most conservative rate with respect to power. This calculation assumed 1:1 individual-level randomization of n=1000 high-risk patients within each of N=32 clinics that will be randomized to receive clinic-level nudges. These power calculations used combined retrospective data from Penn and UW to estimate the average number of patients per clinic and the number of high-risk patients who will be randomized. We expect to have greater power for both comparisons at the replication site which comprises more clinics and patients.

--Statistical Analysis--

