We will test each of the four linear contrasts of the parameters estimated from the GEE model. We will use a Bonferroni correction for the first two contrasts, aligning with how the study was powered (i.e., two-sided significance level of 0.025 for the first two contrasts). We will consider contrasts 3 and 4 as exploratory, and thus we will not correct the corresponding p-values for multiple testing. Results will be reported on the odds ratio scale, including 95% confidence intervals. Confidence intervals for contrasts 1 and 2 will incorporate the Bonferroni correction used for the two tests.

Sensitivity Analyses to Evaluate Model Specifications

As a sensitivity analysis, we will restrict the data to high-risk patients at active clinics and estimate the main effect of intensive vs standard text messaging, specifying an exchangeable working

correlation within clinics. As another sensitivity analysis, we will use an exchangeable working correlation at the clinic level after duplicating each clinic's data, assigning one 1 and one -1 for patients without an individual-level assignment, and removing the record for each high-risk patient an intervention clinic corresponding to the opposite of the individual-level randomized assignment that was received. Duplicated clinics will be treated as independent while observations within clinic will be treated as exchangeable. In this way, duplicated records will be treated as independent. Using this approach, we will re-test the main effect of A_1 , i.e., $2\beta_1$, to evaluate sensitivity to specification of the working correlation. We will use a t-distribution with degrees of freedom equal to the number of clinics (47) minus the number of mean model parameters to construct a confidence interval for $2\beta_1$. If the interval does not include 0 (log odds ratio scale) we will reject the null and conclude there is a significant effect of clinic nudges compared to usual care.

Sensitivity Analyses to Evaluate Protocol Deviations

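### Planned enrolment (79,857) and the power section's sample (66,480) differ by 20% without explanation, and under either total the 99% power stated for comparison #2 is not reached

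*Protocol*

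**What the plan says.** **Enrolment.** Protocol 5.6: "Based off our power calculations and preliminary data work, Penn Medicine is expected to enroll approximately 51,152 patients". Protocol 5.7: "UW Medicine plans to enroll approximately 28,705 patients". Lancaster General Health is the separate replication site and is in neither figure.

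**Comparison #1 (clinic-level nudges against usual care).** The power paragraph of Protocol section 9 assumes "N=48 participating clinics across the two sites, an average cluster size of n=1385 patients" and "an intracluster correlation (ICC) of 0.02". It claims 85% power for a 7-point difference. Section 8.2 allocates clinics 2:1.

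**Comparison #2 (intensification against standard messaging).** The same paragraph gives this comparison its own input: 1000 high-risk patients in each of 32 nudge clinics, randomized 1:1. It claims at least 99% power for a 2-point difference, even at a 50% vaccination rate.

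**Alpha.** Protocol section 9: "we used an adjusted Type I error of 0.025 to account for two comparisons". The SAP (Analytical Plan for Primary and Secondary Outcomes) makes it two-sided: "two-sided significance level of 0.025 for the first two contrasts".

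Neither document relates the site figures in 5.6 and 5.7 to the mean cluster size of 1385.

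**The concern.** Two planning totals for the same two health systems differ by a fifth, although the Penn figure is said to draw partly on the power calculations. A reader cannot tell which total the stated power belongs to.

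The natural next step is to ask which total supports the published power. For comparison #2 the answer is neither. That comparison is individually randomized, so its power depends directly on the number of high-risk patients. At stake is how a null result would be read: the protocol implies a type II error of at most 1% for a 2-point effect, while its own inputs give about 9%.

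**Working it through.** **Step 1: the totals.**
- Sections 5.6 and 5.7: 51,152 + 28,705 = 79,857.
- Power section: 48 × 1385 = 66,480.
- Gap: 79,857 − 66,480 = 13,377, and 79,857/66,480 = 1.201.
- The larger total implies 79,857/48 ≈ 1,664 patients per clinic, or 79,857/1385 ≈ 57.7 clinics.

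**Step 2: comparison #1, the plan's 85%.** Inputs: 32 nudge and 16 control clinics, ICC 0.02, a 7-point difference, two-sided alpha 0.025 (z = 2.241). The documents give no baseline rate, so I vary it.

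Design effect = 1 + (m − 1) × 0.02. Effective sample = (clinics × m)/design effect. Power = Φ[(δ − z·SE₀)/SE₁], with SE₀ from the pooled rate and SE₁ from the separate rates.
- m = 1385: design effect 28.68; effective control sample 16 × 1385/28.68 ≈ 773.
- m = 1,664: design effect 34.25; effective control sample ≈ 777.

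| Assumed control rate | Power, m = 1385 | Power, m = 1,664 |
|---|---|---|
| 0.20 | 93.3% | 93.5% |
| 0.30 | 86.8% | 87.1% |
| 0.35 | 84.6% | 84.8% |
| 0.45 | 82.6% | 82.9% |
| 0.50 | 82.9% | 83.1% |

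The stated 85% is reproduced at a control rate of about 0.30 to 0.35. The choice of total moves power by about 0.1 to 0.3 points, because at this ICC extra patients per clinic add almost no effective sample.

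**Step 3: comparison #2, the plan's 99%.** Inputs: 32 × 1000 = 32,000 (16,000 per arm), 0.50 against 0.52, z = 2.241.
- SE₀ = √(2 × 0.51 × 0.49/16,000) = 0.005589.
- SE₁ = √((0.25 + 0.2496)/16,000) = 0.005588.
- Power = Φ[(0.02 − 2.241 × 0.005589)/0.005588] = Φ(1.337) ≈ 90.9%.

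The stated figure is not reproduced. Variants:
- one-sided 0.025 or two-sided 0.05: 94.7%
- one-sided 0.05: 97.3%
- variance reduced by the factor 1 − ICC for clinic stratification: 91.5%
- 1000 per arm per clinic: 99.8%, but this needs 2000 high-risk patients per clinic, more than the mean cluster under either total.

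**Step 4: the larger total.** Assume the high-risk share is 1000/1385 = 72.2%; the documents do not state a share. Then 32,000 × 1.201 ≈ 38,440 patients, about 19,220 per arm. SE₀ and SE₁ are both about 0.00510, and power = Φ(1.681) ≈ 95.4%. If 1000 per clinic is kept as stated, power stays at 90.9% whichever total is used.

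**Step 5: what 99% would need.** About 26,065 per arm, or 52,130 in all.
- With 66,480 patients, two thirds (44,320) are in nudge clinics of average size. Even if all were high-risk, power would be 97.6%.
- With 79,857, two thirds is 53,238, so 52,130/53,238 ≈ 98% of them would have to be high-risk.

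**Step 6: detectable difference at 99% power with 32,000 patients.** (2.241 + 2.326) × √(2 × 0.25/16,000) = 4.567 × 0.00559 ≈ 0.0255, about 2.6 points.

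**The case against.** An enrolment forecast and a power assumption need not be equal. Section 5.6 cites preliminary data work as well as the power calculations, speaks only for Penn, and is worded as an approximation; section 5.7 gives no basis for UW. So a reader should not infer that the whole 79,857 is claimed to come from the power calculations. Nor does either total govern conduct: patients accrue through eligible visits in a fixed window, and no target or cap is set at either number. All of this stands. It limits the consequence, but a 20% gap is not rounding, and the power section presents its inputs as estimates from retrospective data without mentioning a discount.

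Two stronger readings are tempting, and the documents do not support them.
- **That the mismatch weakens the trial's power.** Expected enrolment exceeds the power sample, so any change is upward.
- **That the mismatch changes, or explains, the power of comparison #2.** That comparison has its own stated input of 32,000. Its power moves only if the high-risk share is assumed to scale with enrolment. The 99% shortfall arises inside the power paragraph and would be there without sections 5.6 and 5.7.

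It is also fair to say that 50% is the worst case. With 32,000 patients, power is 94.8% at a standard-messaging rate of 30%, 98.4% at 20% and above 99.9% at 10%. The protocol's claim, however, is made explicitly for 50%.

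**Conclusion.** The point holds as two linked corrections of stated figures.

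1. The totals of 79,857 and 66,480 cover the same sites, differ by 13,377 patients (20%) and are not reconciled. The difference is favourable, and for comparison #1 it is negligible.
2. The power of at least 99% for comparison #2 is not supported under either total. It is about 90.9% on the stated inputs and about 95.4% if the 1000/1385 share carries over to the larger total.

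These figures rest on two-sided alpha 0.025, a 50% rate, a 2-point difference and equal allocation. The comparison #1 figures also rest on an assumed control rate and equal clinic sizes. Power of 91% is still good. The error lies in the stated figure, and it does not show that the trial is too small.

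**What to change.** State one consistent set of total enrolment, clinic count, mean cluster size and high-risk number for Penn and UW, or add a sentence saying that 1385 is a deliberately conservative input. The clinic count belongs in this set because the SAP gives 45 in its primary analysis text and 47 in a sensitivity analysis, against 48 in the protocol. Sections 5.6 and 5.7 need not be cut to match 66,480 if they are the better forecast.

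Then recompute both powers from that set and state the control rate assumed for comparison #1. For comparison #2, either restate power for 2 points as about 91% (up to about 95% if the high-risk share is assumed to scale), or keep 99% and restate the detectable difference as about 2.6 points for 32,000 patients.

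The cost is a text correction, with no change to procedures or the analysis model. The downside is that the stated power becomes less favourable.

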5.7 Subjects enrolled by Collaborating Researchers

UW Medicine plans to enroll approximately 28,705 patients.

5.8 Accrual

Patients in this trial will accrue based on their eligible visit during the study period. An eligible visit is defined as the patient's first scheduled new or return non-urgent/sick visit in-person at an eligible clinical site during the study window. Patients in all study groups will be enrolled in the trial 4 days before their scheduled eligible visit.

5.9 Key inclusion criteria

Patient Inclusion Criteria

All patients must meet the following criteria to be eligible:

- 1) Age \geq 50 years
- 2) A scheduled new or return (non-urgent/sick) primary care appointment at one of the study practices at the Penn Medicine, UW Medicine, or Lancaster General Health
- 3) Have not received their annual flu vaccine during the active intervention period (September- February)
- 4) Eligible to receive the flu vaccine

For the patient intensification nudge, at least one of the following criteria must be met to be considered high risk and randomized to receive the intensification nudge:

- 1) Age \geq 70 years
- 2) Living in a lower income community (lowest quartile, zip-code based)
- 3) Did not receive a flu vaccine in the previous calendar year
- 4) Self-identifies as Non-Hispanic Black

Clinician Inclusion Criteria

Clinicians must meet the following criteria to be eligible to receive peer comparison feedback:

- 1) Practicing physician (MD, DO) or advanced practice provider (NP, PA) with the exception of residents and fellows
- 2) Have a minimum patient panel of at least 50 patients, and
- 3) Practicing at a clinical site randomized to receive the clinic-level nudge interventions.

